### **2. Accrual**

For this trial, we project that we will screen about 1200 smokers over 63 months (allowing six months to complete follow-up). Based on our varenicline trial with HIV-infected smokers (IRB Protocol #815435) and the present inclusion/exclusion criteria, we expect about one-third of these smokers to be eligible for the trial (n = approximately 415). To be conservative, given the possible health problems evident in this population of smokers, we will project less than 25% of participants will withdraw from the trial and more than 75% of subjects will complete follow-ups to have 300 complete the study. As is advised in smoking cessation trials (Hughes et al., 2003), intent-to-treat will be used for primary analyses, with missing outcome data coded as smokers.

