#### Medical Exclusion Criteria

1. Females who self-report current pregnancy, planning a pregnancy during the study, or currently breastfeeding/lactating.
2. Current diagnosis of unstable and untreated major depression, as determined by self-report & MINI (eligible if stable for at least 30 days).
3. Current or past diagnosis of psychotic disorder, as determined by self-report or MINI.
4. History of heart disease, stroke or MI, unstable angina, or tachycardia (if stable, requires Study Physician approval).
5. Uncontrolled hypertension (SBP greater than 160 or DBP greater than 100) present at Intake.
  - a. Note: If a participant presents with blood pressure greater than 160/100 at sessions occurring on Week 3 (Pre-Quit) or at any other point during the treatment period, they will not be provided with/able to continue on TN unless the study physician grants approval.
6. Previous allergic reaction to TN.
7. History of diabetes (requires Study Physician approval)
8. History of seizures (requires Study Physician approval)
9. History of stomach ulcers (requires Study Physician approval)

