#### 2. Design

**Main Study.** This study will use a prospective observational matched-design to test whether HIV+ smokers (vs. HIV-smokers) are more likely to experience cognitive deficits during nicotine withdrawal and whether these deficits are predictive of smoking relapse. As shown in Figure 1, adult treatment-seeking smokers (N=300; 150 HIV+ and 150 HIV-) will complete this 12-week study, which is divided into two phases: a pre-quit laboratory phase (weeks 0-2) and a treatment phase (weeks 3-12). Subjects will complete two laboratory sessions during the pre-quit phase: once following 24 hours of mandatory smoking abstinence and once while smoking-as-usual (order counter-balanced; abstinence biochemically confirmed). A cognitive task battery assessing working memory, sustained attention, and response inhibition will be administered during each session. During the treatment phase, subjects will receive standard smoking cessation treatment, including six sessions of brief individual counseling (weeks 3-8) and eight weeks of open-label transdermal nicotine (TN) patch treatment (weeks 4-12) [34]. The primary outcomes will be: 1) cognitive performance (e.g., verbal and working memory) following 24-hours smoking abstinence (vs. smoking-as-usual) during the pre-quit phase, and 2) 7-day point-prevalence, biochemically confirmed abstinence rates at end-of-treatment (EOT) for the treatment phase. Since randomization is not possible in this study, we will rely on inclusion criteria and matching to reduce the potential for confounding. More specifically, participants will be

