#### **Transdermal Nicotine (Weeks 4-12).**

All participants will receive transdermal nicotine (TN) to aid in quitting smoking. TN is available over the counter and is very well tolerated. Participants will use “the patch” in a tapering fashion as recommended by the manufacturer. Participants who smoke 10 or more cigarettes per day will adhere to the following dosing guidelines: 21 mg for 4 weeks; 14 mg for 2 weeks and 7 mg for 2 weeks. Participants who smoke between 5 and 9 cigarettes per day will follow a modified

dosing regimen: 14 mg for 6 weeks and 7 mg for 2 weeks. Participants who smoke between 1 and 4 cigarettes per day will also follow a modified dosing regimen: 7 mg for the full 8-week schedule. The 8-week regimen will commence the morning of the 2nd counseling session (**week 4; TQD**). Participants will be instructed not to smoke beginning that morning and apply a patch. Directions and rationale for use will be discussed during the pre-quit counseling session (**week 3**). Use is reviewed at every post-TQD session and TN will be distributed weekly. If a participant does not have enough patches to continue with their treatment schedule (e.g., used two patches in one day should one fall off), additional supplies of nicotine patches may be mailed or picked up by the participant, if appropriate.

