## **Recruitment & Retention Pilot Outcomes**

### Meeting Eligibility Criteria.

The primary outcome is the percentage of subjects who meet final eligibility criteria (i.e., enrollment). We chose this as the outcome based on our data suggesting that subjects who meet these criteria are highly likely to reach ITT status.

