### **Data Analysis.**

[name] will conduct analyses using Stata, SAS, or R-Language software. Preliminary analyses will determine whether data meet distributional assumptions, and use appropriate transformations where they do not. We will also determine whether subject characteristics (e.g., gender, nicotine dependence, depression, NMR) are associated with HIV status or outcomes using either cross-tabulation (chi-square), *t*-tests, or correlations. Variables showing potential to predict outcome ( $p=0.2$ ) will be tested for entry as controlling variables. In the event of items missing at random on survey measures, missing items will be imputed prior to calculating final scores using conditional means, estimated with an iterated version of Buck's method (Gleason and Staelin, 1975). Dropout and missed sessions present a more serious issue. The best way to deal with this more serious missing data is to avoid the problem in the first place by keeping subjects connected to the trial and motivated to complete measures. Our clinical trials have a record of >80% compliance and retention rates, thanks to our monitoring of participants and use of incentives to offset costs for travel. Primary analyses will include all subjects who went through the laboratory phase and began NRT treatment; we will assume those who provide incomplete smoking data are smoking. This assumption is the convention in smoking cessation research, but can attenuate the differences between study groups. We will, in addition, conduct analyses with other missing data assumptions, including a completers only analysis, to examine the sensitivity of the primary findings to our assumptions.

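### Read literally, the primary analysis set drops Aim 1 subjects with complete cognitive data because they did not later start patches; for Aim 2 it is not reconciled with the undefined intent-to-treat statement.

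*Combined protocol and SAP*

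**What the plan says.** Two places describe the primary analysis population.

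- Accrual (Characteristics of the Study Population): "intent-to-treat will be used for primary analyses, with missing outcome data coded as smokers". No denominator is given.
- Data Analysis (Statistical Analysis): "Primary analyses will include all subjects who went through the laboratory phase and began NRT treatment". The same sentence goes on to count those with incomplete smoking data as smoking. It stands ahead of the paragraphs for Aims 1 to 3, and none of those names another set.

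The only other use of the term is in the recruitment pilot outcomes, which say that "subjects who meet these criteria are highly likely to reach ITT status". There it is a status reached after enrolment.

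On timing, the Design section says "Subjects will complete two laboratory sessions during the pre-quit phase", which places the cognitive measurements in weeks 1 and 2. The patch begins on the target quit day in week 4: "Participants will be instructed not to smoke beginning that morning and apply a patch".

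For sensitivity, the plan will "conduct analyses with other missing data assumptions, including a completers only analysis". The separate COVID-19 sensitivity analysis concerns remote visits.

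**The concern.** The Aim 1 outcome is the change in cognitive performance between the two lab sessions. A subject who attends both has a complete outcome two weeks before the first patch. Requiring a patch start removes some of these subjects for something that happens after both exposure and outcome.

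That later event may not be neutral. The protocol's theory is that deficits during abstinence make quitting harder. It speaks of relapse rather than of failing to start, but a subject who did badly when abstinent could plausibly also be less likely to begin. Starters would then show smaller deficits than all subjects tested. This matters most for the Aim 1 paragraph's plan to report the HIV+ group's own deficits with 95% confidence intervals.

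For Aim 2, someone lost between Lab 2 and the quit day is either a smoker in the denominator or absent from it, depending on how the two statements are combined. Not starting also has causes other than choice: for subjects with raised blood pressure the exclusion criteria say "they will not be provided with/able to continue on TN unless the study physician grants approval". The choice carries into Aim 3, which goes ahead only if the Aim 2 effect is significant. No planned sensitivity analysis brings non-starters back; the one that is named, completers only, is narrower still.

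**Working it through.** **1. The plan's own Aim 1 figures.** Inputs from the Power Analysis section: 150 per group, d = 0.4, alpha = 0.01 (taken as two-sided).

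- Noncentrality = 0.4 × √(150/2) = 3.46. Noncentral-t power on 298 df is 80.8%, which reproduces the stated 80%.
- Confidence interval for the HIV+ group: full width 2 × 1.96/√150 = 0.32 SD, as stated; half-width 0.16 SD.

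**2. Effect of keeping starters only (Aim 1).** The documents give neither a non-start rate nor a link between deficit and starting, so both are assumed. Deficits are normal with SD 1, mean 0 in HIV- and 0.40 in HIV+. The probability of starting is 1/(1 + exp(−(a − b × deficit))), with a set so that 80% start overall (a = 1.561 for b = 0.5; a = 1.859 for b = 1.0).

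| Slope b | Start HIV- / HIV+ | Mean HIV- | Mean HIV+ | Raw difference | SD in starters | d |
|---|---|---|---|---|---|---|
| 0 | 80% / 80% | 0 | 0.40 | 0.40 | 1 | 0.40 |
| 0.5 | 81.5% / 78.5% | −0.09 | 0.30 | 0.386 | 0.982 | 0.39 |
| 1.0 | 82.8% / 77.2% | −0.15 | 0.21 | 0.356 | 0.943 | 0.38 |

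Both group means fall, so most of the shift cancels in the contrast. The HIV+ mean falls by 0.10 to 0.19 SD, against a planned half-width of 0.16 SD.

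Over other non-start rates:

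- 5% non-start: HIV+ mean 0.37 (b = 0.5) or 0.35 (b = 1.0); d = 0.40 or 0.39.
- 25% non-start: HIV+ mean 0.27 or 0.16; d = 0.39 or 0.37.

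**3. Power that could be recovered (Aim 1).** If exactly 150 per group start, then 170 lab completers per group (1 − 150/170 = 12% non-start) gives 86.3%, and 200 per group (25% non-start) gives 92.0%. These are upper illustrations. Accrual expects about 415 eligible and 300 completing, so 415 − 300 = 115 losses in all. Losses before Lab 2 cannot be recovered, and losses after patch start are already in the set. Only those between Lab 2 and patch start count, and their number is not given.

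**4. Aim 2 under the two sets.** Abstinence in the wider set = fraction starting × abstinence among starters, with non-starters coded as smoking. Abstinence among starters is taken from one of the plan's pairs: 40% HIV-, 25% HIV+ (15 points, odds ratio 2.00). Start fractions are assumed.

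| Start HIV- / HIV+ | Wider-set rates | Difference | Odds ratio |
|---|---|---|---|
| 80% / 80% | 0.80 × 40 = 32.0%; 0.80 × 25 = 20.0% | 12.0 points | 1.88 |
| 90% / 75% | 0.90 × 40 = 36.0%; 0.75 × 25 = 18.75% | 17.3 points | 2.44 |
| 75% / 90% | 0.75 × 40 = 30.0%; 0.90 × 25 = 22.5% | 7.5 points | 1.48 |

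The starter set shows 15 points in every row.

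**The case against.** The strongest reply is that there is no contradiction. The Accrual section states a principle without a denominator; the Data Analysis section supplies a denominator and the same missing-equals-smoking rule. The second can be read as the working definition of the first, and the pilot's use of the term as a milestone after enrolment supports that. This stands. A reader might infer that the plan promises an analysis of everyone enrolled and then breaks that promise. The documents do not support this, because the term is never defined.

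The restriction may also have been meant for smoking outcomes only. It sits in a discussion of dropout, its second half concerns smoking data, and the Aim 1 paragraph does not mention patches. That is a fair guess at intent, but the sentence speaks of primary analyses without limit and no other Aim 1 set is given.

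For Aim 2, the groups are not randomised ("Since randomization is not possible in this study, we will rely on inclusion criteria and matching"), so intent-to-treat protects no randomised comparison. The aim asks about quitting after standard treatment, so a treated set is a coherent choice. This also stands: which Aim 2 set is primary is partly a choice of estimand.

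Finally, Aim 1 meets its planned power at 150 per group, and the steeper slope is a strong assumption: the odds of not starting rise 2.7-fold per SD. Both points are right and limit the claim.

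**Conclusion.** The point holds. The literal wording makes Aim 1 depend on a week-4 event although its outcome is complete in week 2, and no planned analysis undoes this. It discards usable data and can bias the reported HIV+ deficits: 0.40 SD reads as 0.30 to 0.21 under 20% non-start and slopes of 0.5 to 1.0. The between-group test is little affected (d about 0.39 to 0.38). All of this rests on assumed non-start behaviour; if starting is unrelated to the deficit there is no bias, only lost data.

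Three stronger readings are not supported. Aim 1 is not shown to be underpowered, and any gain is limited to subjects lost between Lab 2 and patch start. Aim 2 is not shown to be biased in a known direction, since unequal starting can widen or narrow the difference. Nor does the point extend to subjects who fail the carbon monoxide check at the abstinent lab session, which the Laboratory Session 1 procedures treat as an eligibility condition.

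What remains for Aim 2 is that the primary set should be unambiguous before the data are analysed, because the choice can move the estimate and decide whether Aim 3 proceeds.

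**What to change.** In the Data Analysis section, define the set by aim.

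- **Aim 1**, including the effects of HIV status on the candidate mediators when reported under Aim 1: all subjects with both lab sessions, whether or not they began patches.
- **Aim 2**: name one primary set before analysis, and make the Accrual and Data Analysis sections agree on it. Report the other as a named sensitivity analysis. The two candidates are lab completers with non-starters coded as smoking, and patch starters.
- **Reporting**: give the number who completed the lab phase but did not start patches, by HIV status.

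The cost is wording and a little more analysis; no new measurement is needed. The wider Aim 2 set will show a slightly lower quit rate.

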10. **HIV-negative only:** Complete an on-site HIV test with a nurse trained to administer HIV testing and to do required reporting and counseling should a participant test positive for HIV.
11. Provide one 10ml blood sample (2 teaspoons) to assess nicotine metabolite ratio (cotinine and 3-hydroxycotinine).
12. Provide one 8ml blood sample (2 teaspoons) for examining biomarkers of neuroinflammation.

**HIV-positive** participants will be asked to provide lab work to confirm recent viral load of less than or equal to 1000 copies/mL and CD4+ counts of greater than or equal to 200 cells/mm^3 within 12 months prior to enrollment. If a participant is unable to provide lab work, their clinic may be contacted to obtain the necessary documentation.

If eligible at this point, subjects will schedule their first laboratory session (Week 1).

**Laboratory Session 1 (Week 1).** This visit should occur within eight weeks of Intake. Allowances may be made for staff or subject scheduling conflicts. This in-person visit is expected to last 1-1.5 hours. During this visit, participants will:

1. Provide urine specimens for drug and (if applicable) pregnancy tests (See Exclusion Criteria above and Measures below).
2. Provide a CO sample.
  - a. During the smoking session: To standardize smoking across participants, they will smoke a cigarette about 30-40 minutes prior to beginning the cognitive task battery, as in our past studies ([name] and Hawk, 2012; [name] et al., 2014; [name] et al., 2013a; Tsaur et al., 2015)
  - b. During the abstinent session: Participants must have CO readings less than 10ppm or less than 50% CO reading taken at Intake in order to be eligible for the study.
3. Complete questionnaires (see Table 1. Study Measures). Measures may be completed remotely via RedCap to reduce the length of in-person tasks.
4. MADRS, YMRS, Bipolar Disorder Additional Screener, if necessary. Screening measures may be completed remotely via RedCap to reduce the length of in-person tasks.
5. Complete a 1-hour battery of computer tasks which may include tasks assessing working memory (n-back), executive function (Stroop task), response inhibition (stop-signal task), and delay discounting.

**Laboratory Session 2 (Week 2).** Participants will complete the same activities they completed at Laboratory Session 1 in the alternate smoking condition. The following activities may also take place:

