## 2. Statistical Analysis

### **Power Analysis and Sample Size.**

Our study is a longitudinal between-subject design that seeks to test the following hypotheses: 1) that HIV+ smokers experience larger abstinence-induced cognitive deficits than HIV- smokers (Aim 1); 2) have lower quit-rates than HIV-smokers following standard treatment (Aim 2); and 3) that the association between HIV status and relapse is mediated by abstinence-induced cognitive deficits (Aim 3). We have designed our study to achieve 80% power, testing at a global  $\alpha=0.05$  for each of the hypothesis families (Figure 1). Our sample size of 300 was determined primarily by Aim 2. Based on prior work, we expect a ~15% difference in abstinence rates between HIV+ and HIV- smokers (Ferketich et al., 2013; Humfleet et al., 2013; Matthews et al., 2013; Silagy et al., 2004). With 150 HIV+ vs. 150 HIV- smokers, we have 80% power to detect a difference of ~15 percentage points in point-prevalence abstinence (60% vs. 45%, 50% vs. 35%, 40% vs. 25%), using a z-test on log-odds with a type 1 error of 5%. For Aim 1, we will test the HIV status by abstinence condition (24-h abstinence vs. smoking-as-usual) interaction for 5 cognitive measures using a linear regression with one between- and one within-subjects factor. We will correct for 5 tests using  $\alpha=0.01$ . We have 80% power to detect medium effect sizes (Cohen's  $d=0.4$ ). For Aim 3, we will test whether abstinence-induced cognitive deficits predict quit rates and, using SEM, test whether cognitive deficits mediate the effect of HIV status on quitting. The primary aim will be to test the overall fraction of the effect mediated, which will be tested at  $\alpha=0.05$ , which gives 80% power to detect small to medium effects ( $d=0.32$ ). For our exploratory aim, the component individual deficits will be treated as secondary and tested individually as part of an exploratory analysis, also with a 5% type 1 error. To characterize cognitive deficits in HIV+ smokers, 150 subjects will give us an estimate for each measure with a 95% CI that is 0.32 standard deviations wide (Upper – Lower limits). We will estimate the within-subject correlation for these as repeated measures, with a 95% CI that is 0.32 wide (Upper – Lower) if  $r=0$ , 0.24 if  $r=0.5$ , and 0.14 if  $r=0.75$ . Power was calculated using PASS software, NCSS, Kaysville, UT.

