**Aim 1.** We will analyze neurocognitive data with multiple linear regression using a GLM framework. The outcomes will be cognitive deficits measured as a change in response values (see **Section D.4.d.** for description) due to abstinence challenge (24-h abstinence vs. smoking-as-usual). The hypothesized interaction effect of HIV+ status by abstinence condition will be tested by including dichotomous predictors, and examining the corresponding *z*-score. Although the groups will be matched on key variables, we may also include a small number of covariates (e.g., nicotine dependence, Shipley IQ) that show potential to control for error, admitted to the model at  $p=0.1$ . In conjunction with Aim 1, we will be estimating cognitive measures for the HIV+ group, within-subject correlations, and deficits that arise from abstinence challenge. We will summarize point estimates and provide 95% confidence intervals.

**Aim 2.** We will analyze point-prevalence quit rates using logistic regression. The hypothesized effect of HIV status (HIV+ vs. HIV-) will be tested by including a dichotomous term using the *z*-score. A small number of other potential controlling variables will be tested for inclusion ( $p=0.1$ ). Outcomes of the logistic regression analyses will be characterized by odds ratios (e.g., odds of quitting smoking) and 95% confidence intervals. Point-prevalence quit rates at EOT are the primary outcome. Secondarily, we will conduct logistic regression analyses for other assessments of quit rates, including prolonged and continuous abstinence.

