**Aim 3.** Assuming that we find a significant effect of HIV+ status on abstinence at EOT, we will use a correlational and regression-based path model approach for examining mediation of HIV status effects (MacKinnon et al., 2007). Candidate mediators include five cognitive performance task measures (Neurocognitive Outcomes and Table 1), and will be represented as pre-post differences, continuously distributed and treated as normal. The effects of HIV status on candidate mediators, and of mediators on outcome will be assessed using a generalized path model (Stata GSEM), with the model reporting standardized coefficients. The path model partitions the effect of group on outcome into direct (and unexplained) effects versus mediated effects. We will then test the overall mediation hypothesis using the proportion of group effect explained [87, 88, 90] and the strength of each mediating pathway as follows. We will estimate the model for HIV status predicting abstinence without mediators, to estimate the direct effect of status in the unadjusted model ( $\hat{\beta}^*$ ). We will then test whether HIV status predicts the candidate mediators, and in turn, test whether mediators predict abstinence in an adjusted group effect model, and estimate the effect of HIV status in the mediator adjusted model ( $\beta^*$ ). Finally, we will calculate the proportion of HIV status effect explained, which is calculated as  $1 - (\hat{\beta}^* / \hat{\beta}^*)$ ; the standard error for this quantity is calculated using the delta method, and the mediation hypothesis will be tested using a *z*-test. The

primary analysis tested at  $\alpha=0.05$  will be global mediation – when all candidate mediators are included in the model, a significant proportion of the HIV status effect will be explained. We will also conduct a secondary analysis using products of the coefficients along each mediating path using a delta-method based z-test.

Exploratory Aim. Using the path model described above we will quantify the proportion of variance explained by each cognitive domain (e.g., executive function, verbal memory, and response inhibition) in the relationship between HIV status and abstinence rates. Since this test is exploratory, we do not have specific hypotheses about which domain will account for more variance and these analyses will be used for hypothesis generating for future work.

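### Session order is counterbalanced but is not a prespecified term in the Aim 1 or Aim 3 models; the cost is a conservative Aim 1 test and an attenuated mediation estimate, not a shown bias

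*Combined protocol and SAP*

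**What the plan says.** - **Design.** Study Design, section 2, has each subject tested once after 24 hours of abstinence and "once while smoking-as-usual (order counter-balanced; abstinence biochemically confirmed". For Laboratory Session 2, Study Procedures says: "Participants will complete the same activities they completed at Laboratory Session 1 in the alternate smoking condition".
- **Aim 1 model.** Power Analysis and Sample Size describes the HIV status by condition test as "using a linear regression with one between- and one within-subjects factor". The Aim 1 paragraph of Data Analysis says: "The outcomes will be cognitive deficits measured as a change in response values". It adds that "we may also include a small number of covariates (e.g., nicotine dependence, Shipley IQ) that show potential to control for error", with entry at p=0.1.
- **Aim 3 model.** The candidate mediators are five cognitive measures that "will be represented as pre-post differences, continuously distributed and treated as normal". The Aim 3 paragraph names no covariates. Its primary test is the proportion of the HIV effect explained with all mediators in the model, and it is run only if HIV status has a significant effect on abstinence.
- **General screen.** The opening of Data Analysis examines subject characteristics. "Variables showing potential to predict outcome" at p=0.2 are then tested for entry.
- **Analysed set.** "Primary analyses will include all subjects who went through the laboratory phase and began NRT treatment".

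No analysis section mentions order, period or sequence of the laboratory sessions. The random order under Neurocognitive Outcomes is the order of tasks within a battery. The one design variable that is added, the pre-/post-COVID indicator, belongs to a sensitivity analysis.

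**The concern.** If people do better the second time they meet a task, an abstinent-first subject's abstinent-minus-smoking score moves one way and a smoking-first subject's moves the other. Counterbalancing makes these shifts cancel in a group mean. It does not remove them from the individual scores.

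The two aims use those scores differently. Aim 1 compares group means, so unmodelled order only inflates the residual variance. Aim 3 uses each subject's score to predict that subject's abstinence, so order acts as measurement error in the mediator. It weakens the mediator-to-abstinence path and pulls the proportion explained, the primary Aim 3 quantity, towards zero.

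**Working it through.** **Inputs.** From the plan: 150 per group; Aim 1 d=0.4 at alpha 0.01; Aim 3 d=0.32 at alpha 0.05. Not in the documents, so assumed: a practice effect g of 0.2, 0.3 or 0.5, in SDs of the change score free of order. Order enters the score as +g or -g, so leaving it out raises the residual SD from 1 to s = sqrt(1+g²).

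**The plan's own figures.** Aim 1: 0.4/sqrt(2/150) = 3.464; Phi(3.464 - 2.576) = 0.813, against a stated 80%. Aim 3, treated as a two-group comparison: 0.32/sqrt(2/150) = 2.771; Phi(2.771 - 1.960) = 0.791, against a stated 80%. Both reproduce.

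**Aim 1.** With an even order split within each HIV group, the estimate and its true variance are unchanged, but the reported standard error is too large by the factor s.

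| Quantity | g=0.2 | g=0.3 | g=0.5 |
|---|---|---|---|
| Reported SE inflated by s | 1.02 | 1.04 | 1.12 |
| True alpha, 2[1 - Phi(2.576s)] | 0.0086 | 0.0072 | 0.0040 |
| Power without order, even split, Phi(3.464 - 2.576s) | 0.80 | 0.78 | 0.72 |
| Power without order, order allocated at random, Phi(3.464/s - 2.576) | 0.79 | 0.77 | 0.70 |
| Power with order | 0.81 | 0.81 | 0.81 |

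The plan does not say which SD its d=0.4 refers to. If that SD already includes order variation, power under an even split is Phi(s(3.464 - 2.576)) = 0.82, 0.82, 0.84 without order and Phi(3.464s - 2.576) = 0.83, 0.85, 0.90 with it.

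**Would the screens admit order?** In Aim 1, if order were offered, z = g·sqrt(300) = 3.46 at g=0.2, which passes p=0.1 with probability 0.97, and with probability about 1 from g=0.3. In Aim 3, a screen against abstinence admits order at about its nominal rate whatever g is (simulated: about 20% at p=0.2, about 10% at p=0.1), because a counterbalanced order is not expected to predict abstinence by itself.

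**Aim 3.** For a single mediator the slope shrinks by about 1/(1+g²) = 0.96, 0.92, 0.80. For the five-mediator test, the simulation assumed:
- abstinence of 30% against 15%;
- one score per task, each with an HIV effect of 0.4 SD and a log-odds slope of 0.3 per SD;
- order split evenly within group;
- a delta-method z-test of the proportion explained, run only when the total HIV effect is significant.

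There were 5,000 replicates per case, with Monte Carlo standard error about 0.007.

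| Tasks with practice | Mediator correlation | Power with order | Without, g=0.2 | g=0.3 | g=0.5 |
|---|---|---|---|---|---|
| 2 of 5 | 0.3 | 0.68 | 0.69 | 0.68 | 0.67 |
| 2 of 5 | 0 | 0.80 | 0.80 | 0.79 | 0.75 |
| 3 of 5 | 0.3 | 0.68 | 0.68 | 0.66 | 0.61 |
| 3 of 5 | 0 | 0.81 | 0.78 | 0.75 | 0.65 |
| 5 of 5 (upper bound) | 0.3 | 0.67 | 0.64 | 0.57 | 0.39 |
| 5 of 5 (upper bound) | 0 | 0.81 | 0.73 | 0.61 | 0.32 |

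With three tasks and correlation 0.3, the median proportion explained falls from 0.47 to 0.45, 0.43 and 0.40.

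**Why report the split.** An order difference between HIV groups would shift the Aim 1 contrast by 2 × g × (difference in share abstinent-first). A hypothetical 10-point difference gives 2 × g × 0.10 = 0.04, 0.06 or 0.10 SD.

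**The case against.** **The Aim 1 screen largely covers it.** The covariate examples are open-ended, and wherever omission costs much, order would pass p=0.1 if offered. This stands for Aim 1. What remains there is that entry is optional and data-driven. It does not help Aim 3.

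**Practice may touch few tasks.** The HVLT-R has alternate forms, delay discounting records hypothetical choices, and Stroop interference is a difference score. That leaves the N-back and the stop-signal task, and the latter has practice trials and an adjusting delay. This stands: two of five is the better-supported case, and there the loss is often undetectable.

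**The Aim 3 sizes rest on assumed inputs.** This also stands. The simulated baseline of 0.68 or 0.81 is not calibrated to the plan's d=0.32 and is no evidence against its stated 80%. The Aim 1 paragraph also refers to a Section D.4.d for the change scores. No section so numbered appears in the documents, so their derivation is not fully visible.

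**Stronger readings that the documents do not support.** A reader might infer that the Aim 1 contrast is biased. With an even split it is not. The documents do not say that counterbalancing is done within HIV group, and at the Bradbury-Sullivan Center Intake and Lab 1 are combined for HIV-positive participants, but no imbalance is shown. A reader might also infer a real loss of sample size in Aim 1. Under an even split the estimate is as precise as with order; only its reported standard error is too large. Finally, the pre-post wording in Aim 3 might be read as session 2 minus session 1. The Aim 1 paragraph defines the deficit by smoking condition, so this is a wording matter.

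**Conclusion.** The point holds as a free improvement of minor to moderate severity. That no order term is prespecified is clear from the text. No stated figure is shown wrong.

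In Aim 1 the consequence is a conservative test with intervals that are too wide: about 1 power point at an assumed 0.2 SD and 9 at 0.5 SD (0.81 to 0.72). If the planned d already includes order variation, the stated power stands and the order term only adds to it.

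Aim 3 carries the weight, because exact balance does not remove the attenuation and no stated screen would reliably admit order. Allowing for simulation error, the power loss is:
- two tasks: about nil at correlation 0.3 and 0.2 to 0.3 SD; about 5 to 7 points if uncorrelated at 0.5 SD;
- three tasks, correlation 0.3: about 2 to 4 points at 0.3 SD and 7 to 8 at 0.5 SD;
- three tasks, uncorrelated: about 6 points at 0.3 SD and 16 to 17 at 0.5 SD.

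Practice in all five tasks is an upper bound. These sizes depend on the assumed practice effect, number of tasks affected, mediator correlation and slopes; the direction does not.

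**What to change.** Prespecify session order (abstinent-first or smoking-first) as a fixed term, exempt from the p-value screens, in the Aim 1 model and in both the mediator and outcome equations of Aim 3. Report the order split by HIV group in the analysed set, that is, those who went through the laboratory phase and began NRT. As wording only, describe the Aim 3 mediators as abstinent minus smoking-as-usual, to agree with Aim 1.

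The cost is plan wording and one degree of freedom per model or equation, out of about 300 subjects. Order follows from the condition run at Lab 1, so no new data are needed.
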